- (E3) how the number of consultations delivered in primary care develops in the first two years after introducing POCUS use in general practice including the variation over time and between GPs.
- (E4) how the GPs' reported effect of POCUS on their clinical decision and patient management in general practice develops in the first year after introducing POCUS use in general practice.
- (E5) the number of unwanted cases associated with the use of POCUS reported by the participating GPs in the first two years after introducing POCUS use in general practice.

Outcomes to assess implementation strategy effects:

- (I1) Adoption: the proportion of participating GPs that adopt the intervention and start using POCUS in their daily practice during the educational interventions (months 1-3).
- (I2) Fidelity (adherence): the proportion of participating GPs that complete the educational elements in the intervention (pre-post tests, webinars, assignments, attendance on seminar days, logbook registrations).
- (I3) Reach (penetration): The proportion of teachers who actively support participants by engaging in the online part of the educational interventions
- (I4) Sustainability (maintenance): the proportion of participating GPs that adopt the intervention and continue to use POCUS in their daily practice following the educational interventions (months 5-6).

Outcomes to inform further development of the implementation strategy

- (D1) Adaptability: the extent to which the teachers and participants find that the implementation of the educational intervention meets local needs
- (D2) Acceptability: the extent to which the teachers and participants find the implementation of the educational interventions is agreeable in terms of content and delivery
- (D3) Feasibility: the extent to which the teachers and participants find the educational intervention to be suitable for implementation
- (D4) Compatibility (appropriateness): the extent to which the teachers and participants perceive the implementation of the educational intervention is in line with the organisation's values, mission, priorities
- (D5) Dose (satisfaction): the extent to which the teachers and participants are satisfied with the amount of support and resources received as part of implementation strategy
- (D6) Complexity: the extent to which the teachers and participants perceive the implementation of the educational intervention as being difficult or complex

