Outcomes to assess the effectiveness of the intervention:

Following the use of POCUS in the general practice consultations the GPs will follow normal procedures for registration of activities in general practice using remuneration codes, fee-specific codes for using POCUS, and referrals in the medical record system. Prior to this study 11 fee-specific codes for 11 different POCUS examinations will be installed in the medical record system. The Primary Sector Data Provider Platform (PLSP) will develop an algorithm that allows for the following data extraction on each participating GP in a given time frame: (1) number of POCUS examinations performed, (2) number of referrals, and (3) number of consultations (outcomes E1-3). PLSP will deliver monthly aggregated data for each participating GP from baseline to 24 months after baseline. These continues data will be summarized to demonstrate variation over time.

For the registration of the clinical effect of POCUS use in the consultation (outcome E4), we will use an adapted version of a questionnaire used in a previous cohort study²⁴. The GPs will be asked to specify the following for each POCUS examination: (1) organs/structures examined with POCUS (drop down menu or free text), (2) whether POCUS use entailed a change in diagnosis (yes/no), (3) whether POCUS use entailed a change in referral (yes/no), (4) whether POCUS use entailed a change in treatment (yes/no), (5) whether POCUS use entailed a change in diagnostic certainty for the GP (yes/no), (6) whether POCUS use was helpful for the GP in terms of making a decision for patient management (5-point Likert scale), (7) whether POCUS use was helpful for the GP in terms of arriving at a diagnosis (5-point Likert scale). GP will assess the questionnaire immediately after performing POCUS during consultations in clinical practice. These categorical data will be collected for each participating GP from day 7 to day 372.

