Data collection participants in course 2: August 30th 2022 to November 30th 2024.

14 Sample size

This is accompanying research and as such no formal sample size calculations are made. Our potential study population is 36 GPs, who have signed up to participate in an ultrasound course organized by PLO-e. We expect a participation rate of 66% corresponding to 21 GPs. Previous cohort studies from Danish general practice have shown that GPs' average use of POCUS corresponds to once a day. With a data collection period of 24 months for participants corresponding to 200 working days, we expect approximately 8400 POCUS registrations in this study.

15 Recruitment

Two ultrasound courses delivering the educational intervention have been included in PLO-e's course catalogue for 2022 and as such all GPs working in Danish general practice has had the opportunity to sign-up for the courses. PLO-e has handled the participant recruitment and registration based on a first-come-first-served principle as well as the financial and practical aspects of organizing and executing the courses. The two ultrasound courses have a total of 36 available spots and all 36 participants are offered the opportunity to participate in the data collection for this study. However, not all participants will be offered financial compensation for participating in the study, as a collective agreement between the Danish regions and the association of GPs only allows for those GPs with in longest distance to a radiology department to have a free course attendance and a fee for performing POCUS during the data collection.

The offer to participate in the study is made upon registration to the course and repeated at the first webinar (day 1). At the webinar participants are informed about the research project and written information about the project including a consent form is distributed to participants. The signed consent forms are collected from participants on the first training seminar (day 7).

Assignment of interventions

16a Allocation Sequence generation

n/a

16b Allocation concealment mechanism

n/a

16c Implementation

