GP registrations: For the GPs' registration of POCUS effect in the consultation (outcome E4), GPs will use paper registrations in logbooks during the educational intervention (day 7 to 96). Here the registrations are made for the GPs own purpose as part of the learning process. Following the educational intervention, we will ask the GPs to continue making these registrations with the purpose of research, using a QR code to access an online questionnaire. The paper registrations will be collected by the research team at the third teaching seminar (day 97) while the online-questionnaire data are collected continuously from day 97 to 372.

For the reporting of anonymously unwanted cases, GPs will have a QR code and a link for an online questionnaire (outcome E5). These data are collected prospectively continuously during consultations from the day 7 – day 829.

GP questionnaire: For the pilottest of a cross-sectional questionnaire exploring burnout, stress and job satisfaction at 3 months (outcome F8), an online questionnaire will be distributed to participants following the third seminar day and a possible reminder will follow after two weeks. The questionnaire collecting background characteristics on participating GPs will be distributed on the first teaching seminar (day 7).

Online platform: For the evaluation of participant adherence (outcome I2) and reach (outcome I3) we will use the registrations on the online platform (Microsoft Teams) supporting the educational intervention. These are collected retrospectively at the end of the educational intervention (day 97).¹²

Process evaluation questionnaire: For the evaluation of implementation of the educational intervention (outcomes D1-11) a questionnaire will be distributed to teachers and participants following the educational intervention (day 97).

18b Data collection - Plans to promote participant retention and complete follow-up

During the study, the principal investigator is available for consultation for the participating GPs in order to resolve any problems or obstacles. Reminders will be sent to the participating GPs reminding them to scan patients and contact the research team in case of problems.

19 Data management

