The data management will follow the rules of the General Data Protection Regulation (GDPR) and the Danish Data Protection Agency. All study data will be stored on a secure server at Aalborg University. Questionnaire data will be collected using the online platform SurveyXact (Rambøll, Aarhus, Denmark). A data management agreement has been made between Rambøll and Aalborg University. At the end of the data collection, data will be moved from SurveyXact to Aalborg University's server.

Register data will be collected by PLSP. Data management agreements between PLSP and CAM AAU will be made prior to the collection of data. PLSP will receive data from the different IT suppliers for the general practice clinics. Data management agreements between the IT suppliers and PLSP as well as the GP clinics and the IT suppliers already exists. For this specific study, we will develop an instruction for the GPs to incorporate in the existing data management agreement prior to the collection of data.

All patient-related data will remain in the GPs clinics until the end of the educational intervention (day 97). No data will be transferred to CAM AAU before legal approval by the health authorities has been obtained.

20a Statistical methods for analysing primary and secondary outcomes.

All statistical analyses will be performed using STATA version 17 (StataCorp, Texas, USA) and analyzed according to a predefined statistical analysis plan, which will be uploaded to clinical Trials.org prior to the analysis of data (24 months after baseline). Data will be summarized and reported using descriptive statistics.

For effectiveness related outcomes E1-E5, frequencies and variance are reported as mean and 95% CI or median and IQR depending on the distribution of data. We will use graphic illustrations to demonstrate change over time. To test if changes over time are significant, we will use repeated measures ANOVA analysis.

For outcomes related to the implementation strategy effects (I1-I4) and feasibility of trial methods (F1-F7), we will report proportions as frequencies, while outcomes related to the implementation strategy (D1-D9) will be reported with an average score and outcomes D10-D11 with a summarized estimate on costs. For feasibility related outcome F8, we will report the questionnaire response rate and the corresponding 95% CI.

20b Methods for any additional analyses (e.g. subgroup and adjusted analyses).

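### Section 20a gives E4, the one effectiveness outcome recorded per scan, a mean and 95% CI without fixing the unit of analysis or allowing for GP; taken over scans, the interval would be too narrow.

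*Protocol*

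**What the plan says.** Section 12 (Outcome measures) defines E4 at the level of the scan: "The GPs will be asked to specify the following for each POCUS examination". Besides the organ examined, the form has four yes/no items (change in diagnosis, referral, treatment and diagnostic certainty) and two 5-point items on helpfulness. On type and window it says: "These categorical data will be collected for each participating GP from day 7 to day 372". Section 18a splits that window into paper logbooks up to the third seminar and an online form afterwards: "the online-questionnaire data are collected continuously from day 97 to 372".

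The same section 12 handles the other effectiveness outcomes differently. E1-E3 arrive as monthly aggregates for each GP, and E5 is reported as a monthly total for each GP. No aggregation step is given for E4. Section 7 shows the same contrast: E1-E3 each include variation between GPs, whereas E4 asks "how the GPs' reported effect of POCUS on their clinical decision and patient management in general practice" develops over the first year and does not mention that variation.

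Section 20a then sets one rule for all five: "For effectiveness related outcomes E1-E5, frequencies and variance are reported as mean and 95% CI". The sentence goes on to allow median and IQR instead, depending on the distribution. Repeated measures ANOVA is named for change over time, and a statistical analysis plan, not shown, is to be uploaded before the analysis.

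Section 14 states that no formal sample size calculation was made. It gives the expected size as 21 GPs and adds: "we expect approximately 8400 POCUS registrations in this study".

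**The concern.** The E4 forms from one GP share that GP's skill, equipment, patients, threshold for scanning and habits in answering, so they are not independent. A rule written for data already totalled per GP is carried over to data that are not. Applied to E4 as collected, the mean with 95% CI treats every form as a separate observation. The median with IQR says almost nothing about a yes/no item, because the median is 0 or 1 (or a tie).

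The share of scans that change diagnosis, referral or treatment is the closest the study comes to a measure of clinical effect. An interval computed over thousands of forms would suggest a precision that about 21 GPs cannot supply.

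A second matter follows from the same gap. A mean over scans weights each GP by the number of forms returned. That is a different quantity from the average GP's share whenever the number of forms is related to the answers, and the protocol does not say which of the two it wants.

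**Working it through.** **Inputs from the protocol.** 21 GPs and one scan per working day (section 14); E4 from day 7 to day 372, which is 365 days (section 12).

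**Inputs assumed.** ICC of E4 answers within GP: 0.01 to 0.20. Spread of forms per GP: equal counts first, then a coefficient of variation (CV) up to 1. The protocol gives neither.

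**The plan's own figure.** Section 14 describes the 24 months as 200 working days. Then 21 x 1 x 200 = 4200, not 8400. The figure of 8400 is reproduced with 200 working days per year: 21 x 1 x 400 = 8400. (Section 14 also says "Our potential study population is 36 GPs" and "We expect a participation rate of 66% corresponding to 21 GPs", but 0.66 x 36 = 23.8 and 21/36 = 58%. The choice between 21 and 24 GPs does not alter the factors below, which depend on forms per GP.) E4 runs for one year, so on the reading that reproduces 8400 there are m = 200 forms per GP and 21 x 200 = 4200 in all.

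**Interval over scans, ignoring GP, share of 50%.** Half-width = 1.96 x sqrt(0.25/4200) = 1.5 points.

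**Interval allowing for GP, equal counts.** Design effect DE = 1 + (m - 1) x ICC = 1 + 199 x ICC. The interval over scans is too narrow by sqrt(DE).

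| Assumed ICC | DE | sqrt(DE) | Half-width needed (points) | Effective number of forms, 4200/DE |
|---|---|---|---|---|
| 0.01 | 2.99 | 1.7 | 2.6 | 1405 |
| 0.05 | 10.95 | 3.3 | 5.0 | 384 |
| 0.10 | 20.9 | 4.6 | 6.9 | 201 |
| 0.20 | 40.8 | 6.4 | 9.7 | 103 |

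With a t quantile on 20 degrees of freedom (2.086) in place of 1.96, the needed half-widths become 2.8, 5.3, 7.4 and 10.3 points.

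**Fewer forms.** If the 200 working days really cover 24 months, year 1 has m = 100 and the factors are 1.4, 2.4, 3.3 and 4.6. If only the online phase is used (275 days, about 150 working days at 200 per year), they are 1.6, 2.9, 4.0 and 5.6.

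**Unequal counts.** DE = 1 + ((1 + CV^2) x m - 1) x ICC. With m = 200 and CV 1 the factor runs from sqrt(1 + 399 x 0.01) = 2.2 to sqrt(1 + 399 x 0.20) = 9.0.

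**Simulation check.** Beta-binomial data with 21 GPs, 200 forms each, true share 40%, 4000 runs. The nominal 95% interval over scans covered the true share in 75%, 45%, 32% and 23% of runs at ICC 0.01, 0.05, 0.10 and 0.20. A t interval on the 21 per-GP proportions covered it in 94% to 95%, and in 95% to 96% with unequal counts (CV 0.5 or 1).

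**Weighting.** In the simulation the five busiest of 21 GPs supplied 24% of forms with equal counts, 40% at CV 0.5 and 56% at CV 1. As an invented illustration, let 5 GPs supply 60% of forms.
- If those five report a change in 50% of scans and the other 16 in 25%, the scan-weighted share is 0.6 x 0.50 + 0.4 x 0.25 = 40%, and the average GP is at (5 x 0.50 + 16 x 0.25)/21 = 31%.
- If the two percentages are swapped, the scan-weighted share is 0.6 x 0.25 + 0.4 x 0.50 = 35%, and the average GP is at (5 x 0.25 + 16 x 0.50)/21 = 44%.

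The gap can go either way.

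**The case against.** The strongest reply is that the protocol nowhere says E4 will be pooled over scans. The sentence in section 20a is a single line for five outcomes, four of which are naturally at GP level. Section 12 says the E4 data are collected for each GP, and repeated measures ANOVA needs a repeatedly measured subject, most plausibly the GP. Taking per-GP proportions first is compatible with the text, and the analysis plan may say so. This stands: a reader might infer that a mean over scans is planned, but the document leaves the unit open. What remains is that section 20a does fix the form of the summary and applies it to the one outcome with no aggregation step, where the unit decides whether the interval is valid.

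Three further inferences are tempting, and the documents do not support them.
- **That the interval will be 3 to 6 times too narrow.** No ICC is given. At 0.01 the factor is 1.7.
- **That a few heavy scanners will set the estimate, and push it upwards.** No spread of scan counts is given, and nothing ties volume to perceived usefulness. Section 12 leaves the choice of patients to the GP, and section 15 gives a scanning fee to only some GPs, so unequal counts are plausible. The direction is not known. Between seminars 1 and 2, section 11a has GPs manage patients without acting on the scan, and forms from that period could lower the share.
- **That section 14 treats 8400 as the E4 sample size.** It disclaims any formal calculation, names 21 GPs first, and refers to 24 months, whereas E4 covers about 12.

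It is also fair to say that a scan-weighted share is a legitimate target for a form completed per examination, so preferring the average GP is a choice of estimand. Finally, the progression criteria in section 16c cover only the I, D and F outcomes. No progression decision hangs on an E4 interval.

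**Conclusion.** The point holds in conditional form. Section 20a gives E4 a summary rule that does not fit data recorded per scan within GPs, and it leaves open the one thing that decides whether the interval is valid. If the mean and 95% CI are taken over scans, the interval is too narrow by a factor of 1.7 to 6.4 for an assumed ICC of 0.01 to 0.20, with 21 GPs and 200 forms each. The factor is smaller with fewer forms per GP and larger with unequal counts. Even the lowest ICC tried leaves a nominal 95% interval with about 75% coverage.

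Whether the scan-weighted share and the average GP's share differ, and in which direction, cannot be settled from the document. The protocol should name the one it means. This should be corrected before the analysis. It does not threaten the study, whose effectiveness reporting is mainly descriptive.

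**What to change.** In section 20a, and in the analysis plan that follows it, give E4 its own sentence stating that its intervals take the GP as the independent unit. Either form will do:
- the proportion per GP for each item, then the mean over GPs with a t-based or GP-bootstrap 95% CI; or
- the scan-weighted share with a GP-clustered, small-sample-corrected 95% CI.

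State which is the main estimate, show the range between GPs for each item, and give the number of GPs beside the number of registrations wherever E4 is reported.

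The cost is small. No new data are needed, because section 12 already has E4 collected for each GP, and the change amounts to a few sentences and a few lines of code. The intervals will be wider. A rule for GPs with very few forms (a stated minimum or shrinkage) has to be set before the data are seen.

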A safety committee will be set up to handle all reports of adverse and suspected adverse events (AEs) and serious adverse events (SAEs). MBJ will head the committee.

Introduction

6 Background and rationale

In 2023/2024 the POCUS IN PRACTICE (PIP) study, a large stepped wedged cluster randomized clinical trial (SW-CRT) will be conducted in general practice in Denmark. The overarching aim of this study is to evaluate the implementation of point-of-care ultrasound (POCUS) in Danish general practice. An educational intervention for this study has been developed and tested in a previous study (Evaluating scanning competence following a structured POCUS training program for general practitioners: A hybrid effectiveness-implementation study: Clinical trials registration: NCT05274581). Since then, the intervention has been further developed and in line with the medical research council's framework for developing and evaluating complex interventions², the intervention is ready for the next stage of evaluation (figure 1).

Figure 1. Flowchart of the study process

OK 22: Projects included in the 2022 collective agreement between Danish Regions and The Danish Association of General Practitioners.
OK 25: The 2025 collective agreement between Danish Regions and The Danish Association of General Practitioners, will possibly include a larger scale implementation of POCUS in general practice depending on the results of the OK22 projects.

7 Specific objectives

Being a hybrid type 2 effectiveness-implementation study³, this study aims to simultaneous assess the clinical effectiveness of the intervention and to measure the impact of the implementation strategy as co-primary aims. The implementation-related outcomes have been developed based on recommendations for implementation strategy measures for use in feasibility and pilot implementation studies⁴.

Outcomes to assess the effectiveness of the intervention:

For GPs attending a 3-months basic POCUS course, we aim to determine:

(E1) how the frequency of use of different POCUS examinations develops in the first two years after introducing POCUS use in general practice including the variation over time and between GPs.

- (E2) how the frequency of referrals for secondary care develops in the first two years after introducing POCUS use in general practice and including the variation in referrals over time and between GPs.

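### Section 20a reports variance as a 95% CI when the mean is used, so no reported statistic directly shows the between-GP variation that E1-E3 set out to determine

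*Protocol*

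**What the plan says.** Section 7 makes between-GP variation part of three effectiveness outcomes. E1 concerns the frequency of POCUS use over two years and E3 the number of consultations; both close with the words "including the variation over time and between GPs". E2 asks for the development of referrals, "including the variation in referrals over time and between GPs".

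Section 20a gives one reporting rule for E1-E5: "frequencies and variance are reported as mean and 95% CI or median and IQR depending on the distribution of data". Two further sentences in 20a deal with time only. One covers graphs: "We will use graphic illustrations to demonstrate change over time". The other covers testing: "To test if changes over time are significant, we will use repeated measures ANOVA analysis".

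Section 12 describes the data behind E1-E3: "PLSP will deliver monthly aggregated data for each participating GP from baseline to 24 months after baseline". Their stated purpose is again variation over time; differences between GPs are not mentioned there. The protocol names no SD, range, between-GP variance component or per-GP display for these outcomes.

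**The concern.** The rule in 20a names variance as something to be reported and offers two ways to report it. Only one describes spread. The IQR shows where the middle half of the GPs lie. The 95% CI of a mean shows how well the average is estimated, and it depends on the number of GPs as well as on how much they differ.

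The shape of the data therefore decides whether the reader sees between-GP spread at all. If one outcome is reported by the first branch and another by the second, their intervals measure different things and cannot be compared as variation. A reader who takes the CI as the stated measure of variance will think the GPs more alike than they are. The study precedes a stepped-wedge cluster trial of the same intervention, so how much GPs differ in POCUS use, referrals and consultations is useful to know, and the protocol says it will determine it.

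**Working it through.** The protocol states no figure for this point, so there is none to reproduce. The check compares the width of the two intervals in 20a when both describe the same set of GPs.

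**Inputs.** Number of GPs: 21 expected (section 14), 20 in the registration table, and 36 if every course participant joins. Section 14 derives 21 from 66% of 36, but 0.66 × 36 = 23.8, so 24 is included too. The between-GP SD is not given, so results are in SD units. Normality across GPs is assumed; it suits the branch in which the mean would be chosen.

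**Formulas.**
- Width of the 95% CI of a mean across n GPs = 2 × t(0.975, n−1) / √n, in SD.
- Width of the IQR under normality = 2 × 0.674 = 1.35 SD, for any n.
- Share of GPs inside the CI = 2Φ(h) − 1, where h is the CI half-width in SD.

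**For n = 21.** t(0.975, 20) = 2.086 and √21 = 4.583. Half-width = 2.086 / 4.583 = 0.455 SD; width = 0.91 SD. Share inside = 2Φ(0.455) − 1 = 35%. IQR width over CI width = 1.349 / 0.910 = 1.48.

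| n | CI half-width (SD) | CI width (SD) | GPs inside CI | IQR width / CI width |
|---|---|---|---|---|
| 20 | 0.468 | 0.936 | 36.0% | 1.44 |
| 21 | 0.455 | 0.910 | 35.1% | 1.48 |
| 24 | 0.422 | 0.845 | 32.7% | 1.60 |
| 36 | 0.338 | 0.677 | 26.5% | 1.99 |

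The spread is the same in every row, yet the CI narrows by 1 − 0.338/0.468 = 28% from n = 20 to n = 36. The IQR holds 50% of GPs throughout.

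**Illustration (assumed values).** With a monthly mean of 20 scans and an SD of 10 across 21 GPs, the CI is 20 ± 4.55, or 15.4 to 24.6. The IQR is 20 ± 6.74, or 13.3 to 26.7.

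**Unit of the CI.** Section 20a does not say whether the CI is built across GPs. If 21 × 24 = 504 GP-months were pooled and treated as independent, the half-width would be 0.088 SD and the interval would hold about 7% of values.

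**Other parts of the plan.** The graphs and the repeated measures ANOVA are assigned to change over time, and section 12 mentions only variation over time. None of them is assigned to between-GP spread.

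**The case against.** The strongest reply is that nothing is lost. If the CI is built across a known number of GPs, then SD = half-width × √n / t, which is 2.20 × half-width at n = 21. That is right, and it rules out the reading that the objective cannot be answered. It does require the reader to know that the unit is the GP, which 20a does not state, and a stated objective should not depend on readers inverting a CI.

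A second reply is that table statistics belong in the statistical analysis plan, which 20a promises before analysis and which may add an SD. This holds for detail on which the protocol is silent. Here the protocol is not silent: it attaches a CI to the word variance. The absence of individual GP curves, percentiles or variance components, on the other hand, is no defect of the protocol.

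Three stronger readings may tempt a reader, and the text does not support them:

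- **Switching between months.** A change from CI to IQR from one month to the next could look like a change in variation. Section 20a does not say that the choice is made month by month; it can equally be read as a choice per outcome.
- **Concealed heavy users.** A few GPs who scan a great deal among many who barely scan would give skewed data. The rule would then point to the median and IQR, which do show spread.
- **A CI 4.3 times too narrow.** This sets 0.91 SD against the 3.92 SD that hold the middle 95% of GPs under normality. The arithmetic is right, but the protocol never offers that range. Against its own alternative, the IQR, the ratio is 1.48.

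Finally, no progression criterion in section 16c uses the E1-E3 summaries. Uptake enters there as proportions (80% for I1, 75% for I4). The consequence is therefore a misreported objective, not a wrong go/no-go decision.

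**Conclusion.** The point holds for the mean branch of 20a. There the protocol assigns a measure of precision to a question about spread, and no other planned summary or analysis is assigned to between-GP variation. At 21 GPs the reported interval would be 0.91 SD wide, against 1.35 SD for the interval used in the other branch, and would contain about 35% of GPs (26.5% to 36% for 36 down to 20 GPs). These figures assume normality across GPs and a CI computed with the GP as the unit. The median branch is sound. The problem is a wrong reporting rule, not lost data, and it should be corrected before analysis.

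**What to change.** In 20a, for E1-E3:

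- Report a measure of spread across GPs (SD, or IQR or range) beside the mean.
- Use the same spread measure at all time points of an outcome.
- Keep the 95% CI only as the precision of the mean, and state that it is computed across GPs.

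Individual GP curves or between-GP and within-GP variance components would be useful additions but are optional. The cost is a sentence or two in 20a, carried into the statistical analysis plan. The register data already arrive monthly for each GP, so nothing new has to be collected.
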